Data Management and processing: [name], the biostatistician, will perform all statistical analyses. All data will be entered using a custom program written for the project. An on site data manager will oversee the data collection and entry, and quality control. The database will be visual dBase for data entry and will be converted to SAS (version 8.2) for statistical analyses. [name] will produce the data source tables, summary data tables as well as perform the designated analyses. All entered data will be manually compared to the source documents for accuracy. Additional checks for consistency within and between records will be built into source documents for accuracy. Baseline and follow-up data will be collected on case report forms.

Power Analysis

This RCT is based on a randomized block design, comparing the treatment group with the placebo group composed of males who all have Klinefelter's syndrome and are between the ages of 4 and 12 years of age. Based on previously published data for word fluency performance in KS males, receiving or not receiving testosterone (25), we performed a power analysis and determined that we will have > 90% power, at alpha = 0.05, two-tailed, to detect significant androgen effects on working memory/executive function for each active treatment group versus the placebo group, with n=20 in each group.

References

5. **Ratcliffe SG** 1982 The sexual development of boys with the chromosome constitution 47,XXY (Klinefelter's syndrome). *Clin Endocrinol Metab* 11:703-16.

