Androgen Effects on Cognition in Klinefelter's Syndrome

NCT #: NCT00348946

Date: January 1, 2011

PROTOCOL: Androgen Effects on Cognition in Klinefelter's Syndrome, Control # 02F476, [name]., Thomas Jefferson University

Specific Aims

Klinefelter's syndrome (KS) (1) is a relatively common genetic disorder that occurs in 1/500 males, is defined by the abnormal chromosome karyotype 47,XXY, and includes a characteristic physical, cognitive, and behavioral phenotype. The KS physical phenotype is based on testicular failure and tall stature. The KS cognitive phenotype includes language-based learning difficulties, dyslexia, impaired attention, working memory, and executive abilities, and diminished muscle tone, strength, and coordination. The KS behavioral phenotype involves poor self-image, shyness and increased social anxiety, starting in childhood.

The KS phenotype may be the result of androgen deficiency in utero, infancy and childhood. Androgen replacement is standard in adolescent and adult KS males but has not been used earlier in childhood. The goal of this randomized clinical trial is to study the effects of childhood androgen replacement on the KS neurocognitive and physical phenotypes. This randomized, placebo-controlled, longitudinal study tests a novel intervention in this population. We propose to replace androgen for two years in KS boys, between the ages of 4 and 12 years, using low, physiologic doses. We predict that multiple facets of the KS phenotype will improve with early androgen replacement: working memory, fine- and gross-motor coordination and speed, as well as self-esteem within the cognitive and behavioral phenotypes and muscle strength within the physical phenotype.

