Klinefelter's syndrome is well suited for interventional studies because the disorder is relatively common in males, testicular failure is nearly universal, and the physical and cognitive phenotypic features have been characterized. Early androgen replacement in physiologic rather than pharmacologic dosages is a reasonable, appropriate, and safe consideration in this population. Therapeutic interventions for this relatively common disorder have not been forthcoming, and this represents a unique opportunity to replace a missing hormone and improve aspects of the cognitive and behavioral outcome. The primary specific aim of this study will test the hypothesis that androgen replacement in childhood is beneficial by comparing cognition and behavior in androgen-treated versus placebo KS groups. If successful, androgen replacement would commence early in childhood rather than adolescence or adulthood in Klinefelter's syndrome.

Specific Aim 1. Early androgen intervention, using a randomized clinical trial and treating for two years. We will evaluate five primary outcome variables: general cognition, language summary score, Working memory/executive function summary score, Motor function summary score, and Self-image and social function summary score.

Hypotheses regarding five primary outcomes:

1. Certain aspects of the KS physical, neurocognitive and behavioral phenotype will improve with childhood androgen replacement therapy.

- a. The working memory summary score will improve after two years in the androgen-treated versus the placebo group.

- b. The motor function summary score will improve after two years in the androgen-treated versus the placebo group.
- c. The self-image summary score will improve after two years in the androgen-treated versus the placebo group.

BACKGROUND AND SIGNIFICANCE

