Androgen replacement in KS males has been associated with improved fluency (39) and relatively increased left temporal cortical volumes (25). Working memory has been also been shown to respond to testosterone in elderly men who receive replacement therapy (46). The cerebral cortex may remain plastic until adulthood, permitting changes to be induced by testosterone. Against early testosterone deficiency being the sole etiology for the KS cognitive phenotype is the model of androgen-deficient males with hypogonadism but normal chromosomes, who do not generally suffer from dyslexia or impaired language abilities.

In contrast, the association between the self-image and social phenotypes in KS and androgen deficiency is stronger. Androgen replacement may help in the areas of distractibility, mood, and psychosocial function (22, 47, 48). Verbal IQs in KS adolescents were positively related to earlier pubertal onset and higher testosterone levels (49). Most KS adults treated with testosterone benefited, reporting improved endurance and strength, concentration, learning ability, and mood (22). In addition, testosterone replacement in normal males with delayed puberty has been associated with improved self-perceived competence (47). What is not yet clear is what the optimal age for initiating testosterone treatment in KS males would be.

VI. Genetic mechanisms

The extra X chromosome in KS is usually acquired though non-disjunction during maternal or paternal gametogenesis, occurring in the egg (40-50%) or the sperm (50-

60%), or through an error in mitotic division in the zygote (50-52). Maternal inheritance of the extra X results from non-disjunction in the first (70%) or second (20%) meiosis or as a post-zygotic mitotic error (10%), with increased maternal age and reduced recombination also occurring (51).

VII. Early androgen replacement in KS

In summary, the hormonal and genetic contributions to the KS phenotype remain to be defined more clearly. Early diagnosis, together with early parental education and counseling, and earlier testosterone replacement may contribute to positive adjustment and reduce the negative social, emotional, and education impact of KS. Further studies linking the hormonal and genetic mechanisms will increase our understanding of the pathogenesis of KS and will permit more specific genetic counseling and interventions.

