Post-Study Visit: Per the recommendation of the Data Safety and Monitoring Board (DSMB) all study participants will be invited back for a post-study visit. This visit will occur approximately 6-28 months post-study for patients who have enrolled in the study. The post-study visit will include a history, physical examination, fasting blood work, bone age x-ray, photographs, and cognitive testing. Patients will be reimbursed \$50.00 for completion of the visit. Patients who are unable to travel to a post-study visit or who live farther than driving distance will be asked to have a blood sample drawn locally and sent to our office in Philadelphia.

ANALYSIS

The analysis will be performed in consultation with the statistician, [name] who has been collaborating with [name] for the past 15 years. The analyses described below will include 2 groups of KS boys. All results will be based on gender and age-specific standardized scores. Analysis for safety will be performed at 3, 6, 12, 18, and 24 months and an efficacy analysis for summary scores encompassing all cognitive and behavioral variables will be performed at 12 and 24 months.

I. Safety: An analysis of safety parameters will be performed for the 3, 6, 12, 18 and 24 month values based on a two-way ANCOVA, adjusting for baseline values, comparing the active treatment group versus the placebo. The safety parameters are: systolic and diastolic blood pressure, HDL, LDL cholesterol, liver function (ALT), bone age advancement, or signs of puberty (pubic hair).

II. Primary efficacy (Hypotheses 1 a,b,c): The analysis comparing androgen-treated to placebo-treated KS subjects for the one and two-year measurements will be based on the analysis of covariance (ANCOVA). We will perform a two-way ANCOVA for the five primary outcome measures at 12 and 24 months, comparing the treatment group versus the placebo, adjusting for baseline values and socioeconomic status. There will be a total of 5 summary scores. Each score will be the sum of component z-scores based on gender and age-specific normative values. The summary scores include 1. General cognition, 2. Language, 3. Working memory/executive function and attention, 4. Motor function, and 5. Self-image and behavior. The alpha level for statistical significance will be set at 0.01 for each of the five primary outcome results.

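### Five primary scores are each tested at a fixed 0.01; Holm's procedure over the same five would gain power at 24 months within the same error bound

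*Combined protocol and SAP*

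**What the plan says.** Specific Aim 1 names five primary outcomes: "We will evaluate five primary outcome variables: general cognition, language summary score, Working memory/executive function summary score", then the motor and self-image scores. The list beneath is headed "Hypotheses regarding five primary outcomes" but contains only three specific hypotheses, all at two years. Hypothesis a reads: "The working memory summary score will improve after two years in the androgen-treated versus the placebo group". Hypotheses b and c make the same claim for motor function and for self-image.

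The opening text of the Specific Aims predicts gains in the same areas: "working memory, fine- and gross-motor coordination and speed, as well as self-esteem within the cognitive and behavioral phenotypes". It adds muscle strength, which the outcome list places inside the motor score. General cognition and language are not named in that prediction.

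Analysis, section II (Primary efficacy) refers in its heading to hypotheses 1 a, b and c. It then plans an ANCOVA of all five scores at 12 and at 24 months and states: "The alpha level for statistical significance will be set at 0.01 for each of the five primary outcome results". No ordering of the scores, step-down rule or passing on of alpha is described, and no overall alpha is stated.

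**The concern.** The hypotheses and the list of primary endpoints do not match. Three scores carry a prediction, yet each must pass a threshold set by dividing alpha among five. Two of the five shares (0.02 of an inferred 0.05) are tied to general cognition and language, and nothing is handed on when another score succeeds. Suppose p = 0.012 on motor function and p = 0.004 on working memory. The plan would call motor function negative, although a step-down test over the same five scores would declare it positive. What is at stake is some power on the scores the trial makes predictions about, not the validity of the test.

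**Working it through.** **Inputs from the document.** Five scores at 0.01 each (Analysis, section II). Three specific hypotheses at two years (Specific Aim 1). A target of 120 patients in two groups (Study Population).

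**Assumptions.** 60 per arm, because the allocation ratio is not stated. Effects of 0.4 to 0.6 SD, because the document gives no effect size. No gain from baseline adjustment, because no correlation is given.

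**1. The alpha split.** 5 × 0.01 = 0.05 at one time point. If the tests were independent, 1 − 0.99⁵ = 0.049. The two scores without a hypothesis hold 2 × 0.01 = 0.02, or 40%.

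**2. The plan's power figure.** The Power Analysis claims more than 90% power with 20 per group at two-sided 0.05. It cannot be reproduced without an effect size. The effect giving exactly 90% is d = (1.960 + 1.282) × √(2/20) = 1.025.

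**3. Power under the current rule.** Normal approximation: power = Φ(d√(n/2) − 2.576), with √(60/2) = 5.477.

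- d = 0.4: Φ(2.191 − 2.576) = 35.0%
- d = 0.5: Φ(2.739 − 2.576) = 56.5%
- d = 0.6: Φ(3.286 − 2.576) = 76.1%

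A noncentral t calculation gives 33.9%, 54.9% and 74.7%.

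**4. Holm over the same five.** Order the p-values from smallest to largest and compare them in turn with 0.05/5 = 0.01, 0.05/4 = 0.0125, 0.05/3 = 0.0167, 0.05/2 = 0.025 and 0.05, stopping at the first failure. Every threshold is at least 0.01. A score with p ≤ 0.01 therefore passes, because every smaller p-value has passed too. Holm cannot reject less than the fixed rule, and it keeps the family-wise error at or below 0.05.

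**5. Size of the gain.** I simulated five correlated z-tests (common correlation 0, 0.3 and 0.5), with equal effects on the three hypothesised scores and none on the other two. Average power per hypothesised score:

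| Effect, 60 per arm | Fixed 0.01 | Holm over five | Gain (points) |
|---|---|---|---|
| 0.4 SD | 35% | 37.4–37.7% | about 2.5 |
| 0.5 SD | 56.5% | 60.2–60.5% | about 4 |
| 0.6 SD | 76% | 79.6–80.2% | about 4 |
| 1.0 SD | 99.8% | 99.9% | about 0.1 |

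The chance of at least one rejection does not change, because the first threshold is 0.01 under both rules. The chance of a false rejection on either of the two null scores rises from about 2% to 3–4% at 0.4 to 0.6 SD, still inside 5%.

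**6. For comparison: three primaries at 0.05/3 = 0.0167.** By the same formula with 2.394 in place of 2.576, power is 42.0%, 63.5% and 81.4%, which is 5 to 7 points above the current rule. The noncentral t figures are 41%, 62% and 80%, against 34%, 55% and 75%.

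**The case against.** An equal Bonferroni split over five pre-named primaries is a conventional and conservative rule, and a two-sided test needs no directional prediction. That stands: at one time point the plan's rule is valid.

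A reader might go further and infer that the protocol expects no effect on language or general cognition, so that two-fifths of the alpha is wasted and those scores must be demoted. The sentence most likely to prompt this says that androgen-deficient males with normal chromosomes are people "who do not generally suffer from dyslexia or impaired language abilities". That sentence argues only against testosterone deficiency as the sole cause. The same part of the Background (section V) leaves the cause of the reading and language deficits open, links androgen replacement with better fluency, and reports that verbal IQ was higher with higher testosterone. The primary specific aim concerns cognition and behavior in general. The protocol therefore makes no specific prediction for these two scores; it does not predict a null result. Keeping them primary is a defensible choice, and demoting them gives up confirmatory claims in exchange for power elsewhere.

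It is also fair to object that the gain is small and depends on assumed effects. With 60 per arm and the effect of about 1.03 SD implied by the Power Analysis, it disappears. But that effect is derived from a claim about working memory/executive function alone, and nothing in the document supports it for the motor or self-image scores.

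Finally, no overall alpha of 0.05 is stated, and the scores are tested at two times. If both times count, the alphas sum to 10 × 0.01 = 0.10. This stands as a limit: the equality of error bounds is claimed at 24 months only.

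**Conclusion.** The point holds as one of efficiency. The fixed 0.01 is valid at a single time point, but Holm over the same five scores dominates it: it never rejects less and has the same 0.05 bound. The gain is about 2 to 4 points of average power per hypothesised score for effects of 0.4 to 0.6 SD, and is negligible near 1 SD. This rests on 60 per arm, equal effects on the three hypothesised scores, none on the other two, and an overall 0.05 inferred from the split. The mismatch between five primary outcomes and three hypotheses is a matter of clarity. It does not show that the analysis is wrong or that any endpoint must be dropped. That power was computed at 0.05 while tests run at 0.01 is a separate matter, which Holm does not settle.

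**What to change.** In Analysis, section II, replace the fixed 0.01 with Holm's step-down procedure over the same five summary scores, applied at 24 months, the time the hypotheses name, with a stated total two-sided alpha of 0.05. State the role of the 12-month tests as well, since the bound above covers 24 months only. In Specific Aim 1, either add hypotheses for general cognition and language or say that these two are tested without a specific prediction.

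The cost is wording plus one drawback: simultaneous confidence intervals that match Holm's decisions are less simple than the 99% intervals that go with a fixed 0.01. The post-study visit text suggests that boys have already been enrolled, so the change should be made and dated before treatment codes are broken.

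If the sponsor prefers, the three hypothesised scores could be the only primaries at 0.0167 each, with the other two secondary. That buys more power, but a finding on general cognition or language would then no longer be a primary result.

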The KS boys will be seen at 3-6-month intervals for the two-year duration of the study. On each visit, boys will receive a careful history and physical examination to include assessment of Tanner staging (73) for pubic hair development (Tanner 1 = prepubertal-Tanner 5 = fully mature) and measurement of penile length and testicular volume. At baseline, three, and every six months thereafter, we will measure height, weight, bone age (X-ray); fasting blood work to include complete blood count, serum glucose, liver function tests (SGPT), lipid panel, thyroid studies, testosterone, and free testosterone (the active form of testosterone) levels. LH, FSH and estradiol will be measured yearly. At baseline and after one year, each boy will undergo a battery of cognitive tests that will take approximately 5 to 7 hours (see below).

The form of androgen will be the oral, nonaromatizable androgen oxandrolone. This androgen is FDA-approved for the indication of wasting and has been used safely for the past 30 years to stimulate growth in girls with Turner syndrome without virilization or major side effects. The dose, 0.06 mg/kg/day, was chosen because of the extensive previous experience with the dose of 0.06 mg/kg/day used in girls with Turner syndrome. Children will be monitored closely for signs of virilization including acne, voice changes,

development of pubic hair, and excessive bone age advancement. Since oxandrolone is nonaromatizable and cannot be converted to estradiol, we do not expect any feminizing side effects such as breast development to occur.

Safety results necessitating an approximate 10-50% reduction in medication dose or stopping the medication:

1. Bone age advancement exceeding 12 months per 6-month interval, with bone age exceeding chronologic age.
2. Signs of early pubertal development for age, including pubic hair development in boys less than 8 years of age.
3. Systolic blood pressure exceeding 95th %ile for age.
4. Diastolic blood pressure exceeding 95th %ile for age.
5. LDL cholesterol greater than 159 mg/dl.
6. HDL-C less than 20 mg/dl.
7. SGPT exceeding twice the upper limit of normal.
8. Dose can be lowered at the discretion of the investigator for other reasons such as rapid growth.

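### From 6 months on, the safety ANCOVA estimates the regimen with its dose cuts, and no by-arm count of limit crossings or dose cuts stands beside it

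*Combined protocol and SAP*

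**What the plan says.** Procedures, section IV (Clinical trial substudy), carries a list headed "Safety results necessitating an approximate 10-50% reduction in medication dose or stopping the medication". Its first five items are "Bone age advancement exceeding 12 months per 6-month interval, with bone age exceeding chronologic age"; "Signs of early pubertal development for age, including pubic hair development in boys less than 8 years of age"; "Systolic blood pressure exceeding 95th %ile for age"; "Diastolic blood pressure exceeding 95th %ile for age"; and "LDL cholesterol greater than 159 mg/dl". Items 6 and 7 set limits for HDL (below 20 mg/dl) and SGPT (above twice the upper limit of normal). Item 8 leaves other reductions to the investigator.

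The text after the list gives the tablet steps (3.75 to 2.5 mg, 2.5 to 1.25 mg). It allows one reduction per visit and does not exclude further reductions at later visits.

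Analysis, section I (Safety): "An analysis of safety parameters will be performed for the 3, 6, 12, 18 and 24 month values", by ANCOVA of active treatment against placebo, adjusted for baseline. The variables are named: "The safety parameters are: systolic and diastolic blood pressure, HDL, LDL cholesterol, liver function (ALT), bone age advancement, or signs of puberty (pubic hair").

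The plan does not say how values after a reduction or stop are treated. It specifies no comparison of the arms on limit crossings, reductions or stops.

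**The concern.** A boy whose blood pressure, lipids or ALT rises past a limit gets less drug, or none, and his next value of the same variable is measured under that lower exposure. The later visit means therefore mix boys on the assigned dose with boys who left it because of the outcome being analysed. If the drug harms a minority, those are the boys whose contribution shrinks.

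The protocol says that success would move androgen replacement into early childhood. A flat 24-month comparison could then be read as evidence that 0.06 mg/kg/day is safe, when it shows that the dose plus its reduction rule left little difference in means. How many treated and placebo boys reached a protocol-defined limit is basic safety information, and the plan does not ask for it.

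**Working it through.** **1. Overlap of triggers and analysed variables.**

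| Dose-cut criterion | Analysed in Analysis I | Likely to fall back after a cut |
|---|---|---|
| 1 Bone age | yes | not if cumulative |
| 2 Early puberty, pubic hair | yes | not stated |
| 3 Systolic pressure | yes | plausible |
| 4 Diastolic pressure | yes | plausible |
| 5 LDL | yes | plausible |
| 6 HDL | yes | plausible |
| 7 SGPT (ALT) | yes | plausible |

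The overlap is 7 of 7. The last column is judgement, not text.

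**2. Size of a cut.** 1 − 2.5/3.75 = 33%; 1 − 1.25/2.5 = 50%. This reproduces the upper end of the protocol's 10-50%. The lower end cannot be checked because no rounding rule is given. Two successive steps leave 1.25/3.75 = 33% of the dose.

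**3. Visits affected.** The 3-month value precedes any cut made on follow-up results, and a triggering value still counts at its own visit. Dilution starts at 6 months.

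**4. Inputs for the size.** From the documents: 120 boys, two arms, five visits, and the 95th-percentile limit for blood pressure. Assumed: 60 per arm (ratio not stated), two-sided 0.05 (no safety alpha is given), correlation 0.6 between visits, effect proportional to current dose and complete by 3 months, cuts cumulative over visits, no dropout. Each scenario used 1,500 simulated trials.

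**5. Hand check without cuts.** Residual variance after baseline adjustment is 1 − 0.6² = 0.64. If a fraction f of treated boys shifts by δ, the mean difference is fδ and the treated-arm variance gains f(1 − f)δ².
- f = 0.25, δ = 2: difference 0.50; SE = √[(0.64 + 0.75 + 0.64)/60] = 0.184; power = Φ(0.50/0.184 − 1.96) ≈ 0.78. Simulated: 0.77-0.79.
- f = 1, δ = 0.5: SE = √(2 × 0.64/60) = 0.146; power = Φ(0.50/0.146 − 1.96) ≈ 0.93. Simulated: 0.93.

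**6. With cuts, +2 SD in 25% of treated boys, ANCOVA power by visit.**

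| Cut at each crossing | 3 mo | 6 mo | 12 mo | 18 mo | 24 mo |
|---|---|---|---|---|---|
| 33% | 0.79 | 0.63 | 0.52 | 0.45 | 0.40 |
| 50% | 0.78 | 0.55 | 0.41 | 0.34 | 0.27 |
| Stop | 0.78 | 0.21 | 0.12 | 0.09 | 0.07 |

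Separate runs gave 0.38-0.42, 0.28-0.29 and 0.06-0.07 at 24 months. The 24-month difference falls from 0.49 SD to 0.28, 0.22 and 0.06 SD, so 57%, 45% and 12% of it remains. Fisher's exact test on ever crossing the limit keeps 0.58-0.61 throughout.

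**7. Other harms.**
- +2 SD in 20% of boys: 24-month ANCOVA power 0.62 without cuts; 0.32, 0.21 and 0.05 with 33%, 50% and complete cuts. Ever crossing (two-proportion z-test; 30% against 15% of boys): 0.49-0.52.
- +1.5 SD in 15%: 0.28 without cuts; 0.16, 0.13 and 0.06 with them. Ever crossing (Fisher): 0.16-0.17.
- +0.5 SD in every boy: 0.93 without cuts; 0.83, 0.83 and 0.68 with them. The difference falls from 0.50 to 0.43, 0.41 and 0.36 SD, so 86%, 82% and 72% remains. Ever crossing: 0.58-0.63 by the z-test, about 0.50 by Fisher's test.

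**The case against.** A reader might infer that a real harm can vanish from the safety analysis, that the ANCOVA is invalid, or that a count of crossings should replace it as the main comparison. The documents support none of these.

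- **Five visits are planned, not one.** In the 25% scenario the 3-month test (about 0.78) beats the crossing test (0.58-0.61). Requiring p < 0.01 (0.05/5) at any of the five visits gives about 0.70, 0.66 and 0.56 with 33%, 50% and complete cuts, which matches or nearly matches the crossing test. This assumes the full effect by 3 months; a slowly building harm would not have that protection.
- **ANCOVA is better for a shift shared by all boys**: 0.68-0.85 with cuts, against about 0.50 for Fisher's test. Demoting it could lose power.
- **The simulated limit fits blood pressure only.** LDL, HDL and SGPT have fixed cut-offs whose z-values are not given. With a limit at z = 3 (assumption), few boys cross. A +0.5 SD shift then keeps ANCOVA power at 0.91-0.92 while the crossing test has almost none. For +2 SD in 25% with 50% cuts, ANCOVA has 0.63 and the crossing test 0.45.
- **Bone age already gained does not reverse**, and nothing says pubic hair regresses. The mechanism is weak there unless bone age is analysed per interval, which the plan does not state.
- **Other safeguards exist**: a study-stopping rule for severe liver changes or hypertension, ongoing blinded review by the PI, a DSMB, and unspecified summary tables.

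The first four points limit the size and rule out replacing the ANCOVA. The last does not close the gap: the stopping rule counts patients without regard to arm, the PI's review is blinded, and no by-arm comparison of crossings is specified for the DSMB or the tables.

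**Conclusion.** The concern holds in a limited form. From 6 months on, the planned ANCOVA is a valid comparison of the regimen with its dose cuts, but it understates reversible harm (blood pressure, lipids, ALT) at the assigned dose. The loss is large when harm is concentrated in a minority: about 0.78 to 0.4, 0.3 and 0.07 at 24 months in the 25% scenario. It is modest for a shared shift: 0.93 to 0.83, 0.83 and 0.68. The 3-month comparison is intact. All sizes rest on the assumed effect, correlation, limit and allocation; the documents fix only the direction.

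The omission of by-arm counts of crossings, reductions and stops is a fact of the text and cheap to repair. The repair is an addition, not a substitute for the ANCOVA.

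**What to change.** In Analysis I:

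1. Keep the ANCOVA at all five visits. State that values after a reduction or stop are retained, and label the result as the effect of the regimen with dose reductions.
2. Add, by arm, the number of boys who ever meet each of criteria 1-7 by 24 months, with an exact test or time to first occurrence. Give the boys at risk as denominator, since the pubic-hair part of criterion 2 names only boys under 8.
3. Add, by arm, the number with any dose reduction or stop, with the reason. Item 8 and the weight-based dose cap can also lower the dose.
4. State that a non-significant late-visit ANCOVA alone will not be read as evidence of safety.

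The cost is SAP wording, one extra table and a few more safety comparisons, with low power where a limit is rarely crossed. Crossings can be derived from scheduled measurements. The protocol mentions pill counts and study cards but does not say that dose changes are recorded, so the case report form should be checked for this. No dose rule changes.
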